8.6 SITE TERMINATION OR STUDY TERMINATION

A site or study may be terminated. When this occurs all subjects at the site will be withdrawn and documented as early termination. Reasons for site or study termination may include, but are not limited to the following:

- Administrative Concerns (e.g., inadequate patient enrollment, investigator/institution non-compliance, change of business strategy, etc.);
- Safety Issues, including those due to non-compliance, which substantially affect the risk to benefit ratio of the study subjects at a site or for the study as a whole; and
- Regulatory Body Mandate(s).
- The Investigator has the right to terminate their participation at any time. Should this be necessary, procedures for termination will be provided by the Sponsor.

8.7 SUBJECT COMPLIANCE

Study site personnel will make preemptive contact with subjects as necessary to ensure compliance with the follow-up schedule.

9.0 STUDY PROCEDURES

9.1 PROCEDURE DESCRIPTION

A multi-disciplinary team at the site will determine with the help of imaging, whether a patient is suitable for local ablation therapy, and the type of ablation procedure that is required, based on the stage, location and cell types associated with the liver tumor. Potential candidates for microwave ablation will undergo liver, renal function, coagulation, Alpha-fetoprotein (AFP) and CBC tests before the procedure to ensure that they will have adequate liver capacity following the ablation.

[figure not shown]
Microwave Ablation Procedure

All ablations will be performed under general anesthesia with deep sedation via percutaneous approach by trained interventional radiologists who are experienced with tumor ablation. Microwave ablation is a minimally invasive procedure that uses electromagnetic waves to generate tissue necrosis in the liver in this study. Using contrast-enhanced ultrasound imaging guidance, a small probe is inserted percutaneously into the lesion.

The ablation will be performed with a single high-powered, gas-cooled, multiple antenna-capable microwave system (NeuWave Medical's Certus 140™ 2.45 GHz Ablation System) with single or multi-probe antennas, according to the IFU and the performing physician's clinical judgment. Electromagnetic waves are delivered to the tissue, producing frictional heating to generate tissue necrosis at $> 60^{\circ}\text{C}$. Duration of treatment and power application will be determined by the performing physician based on manufacturer guidelines, with adjustment for tumor size, proximity to vulnerable structures, and real-time intraprocedural monitoring. Antenna placement will be performed under real-time contrast-enhanced ultrasound imaging guidance. Single or multiple ablation sessions may be done in one procedure. It is suggested that the physician considers using more than one probe for lesions ≥ 2 cm.

At the end of the ablation, contrast-enhanced MRI and CT scans will be done to confirm the completion of the ablation procedure (up to 4 days after the date of the ablation procedure). According to the standard practice at the site in Korea, ablation confirmation will be classified as:

- complete tumor ablation with adequate margin
- complete tumor ablation with insufficient margin
- incomplete tumor ablation.

10.0 STUDY DEVICES

For this study, medical devices will be provided to the site by the Sponsor and will be used according to the site's standard of care (SOC) and in accordance with manufacturer design specifications, product instructions and guidelines. Any one of the following devices will be applicable for documentation in this study:

10.1 PRODUCT OVERVIEW

10.1.1 System Overview

The system has a single 2.45 GHz signal microwave source generator and three (3) independent microwave amplifiers, each capable of producing up to 140W each. Generator power is limited based upon the number of probes selected and the types of probes used. One touch-screen user interface controls the system. The User Interface can be set for either Ablation Mode or Surgical Mode. Up to three (3) microwave ablation probes can be connected to and powered by the system at one time. An intermediate junction box or Power Distribution Module (PDM) reduces system set up complexity.

10.1.2 Cooling System Overview

A CO₂ based cooling system ensures the non-active portion of the probe does not exceed temperature requirements. Additionally, the CO₂ enables the Tissu-Loc function, which can be used to adhere or stick the probe in place prior to starting ablation therapy. This function is similar in use to the stick function available on cryogenic ablation systems.

The system uses two (2) E-sized CO₂ cylinders. When a tank in use empties, the system will automatically switch to using the other tank and notify the user to replace the empty tank.

The cooling system regulates the flow of high pressure CO₂ in a cooling gas tube to the PDM and eventually to the probe. Inside the tip of the probe, the cooling gas tube expands from high pressure to low pressure. As the gas pressure reduces quickly, the Joule-Thompson effect causes the probe shaft to cool. This is used for both the Tissu-Loc™ function and to keep probes at a safe temperature while energy is being delivered to the patient.

The PDM is designed to improve the usability of the system by reducing set-up complexity while also helping to minimize the cabling from the probe to the generator. The PDM also allows a larger, lower-loss cable to be used between the microwave generator and PDM. The increased efficiency of the larger cable and PDM allow more power to be safely sent to the ablation probe without an unsafe heating of the probe cable or handle.

System performance is constantly monitored. The Certus 140 Ablation System will automatically discontinue delivering microwave energy in the event of system failures.

10.1.3 Probes Overview

Probes are provided sterile and are intended for single patient use only. Ablation probes are comprised of a sharp trocar on the end of a cannula, a probe handle, a 1.4-meter cable, and a connector assembly.

Each probe contains three (3) temperature measurement sensors that help monitor performance and ensure patient and operator safety. Additionally, the different percutaneous ablation probes have been designed to optimize the energy transfer efficiency from the probe into different types of tissue based on known electrical properties of each tissue.

The ablation probe assembly contains 4 main sections: a handle, a cannula, a radiating section and a faceted tip for insertion. The probes have a triaxial antenna design. The triaxial antenna design is created from a coaxial monopole antenna passed through a hollow needle. The needle creates the triaxial structure and its tip is positioned approximately $\frac{1}{4}$ of a wavelength proximal to the monopole base. This positioning improves antenna efficiency and reduces fields flowing back on the coaxial outer conductor. In turn, more energy is deposited in the tissue. Additionally, different ablation probes have been designed to optimize the energy transfer efficiency from the probe into different types of tissue based on known electrical properties of each tissue.

Models CertusLK and CertusPR have either a 17-gauge or 15-gauge cannula and are available in 15 cm and 20 cm lengths. These probes have a cable length of 1.4 m.

CertusLK probes are designed to perform optimally, in terms of efficiently transferring energy into tissue, in liver and kidney tissue.

The antenna of the CertusPR probe is designed to limit the length of the ablation for instances when a shorter ablation zone is desired. CertusPR Probes were developed to provide physicians with an additional ablation probe designed specifically for ablating smaller lesions. The CertusPR probes are designed to produce ablations that quickly encompass the tip of the probe while limiting the overall length of the ablation. CertusPR probes will enable physicians to ablate smaller lesions while limiting necrosis of adjacent tissue when compared to other Certus probes.

An accessory, a small plastic probe clip that can hold two 17-gauge probes and allow the user to easily hold both while performing planar coagulation, is available.

10.2 PACKAGING AND LABELING

During this study, the study devices will be cleared for marketing by the Ministry of Food and Drug Safety (MFDS) in Korea, and are labeled in accordance with the Medical Device Act⁵¹,⁵². They will be used in accordance with product labeling and IFU.

10.3 PRODUCT ACCOUNTABILITY

All devices must be stored in conditions according to product labeling and IFU. It is the responsibility of the Principal Investigator to ensure that devices are stored correctly at the site.

The Principal Investigator or responsible person designated by the Principal Investigator must account for all study devices throughout and, at the end of, the clinical study. During the course of the study, the study ablation probes must be stored in a locked or secure access location. An inventory record must be maintained of all devices received, used or returned during the clinical trial. Details of the product code and lot numbers must be documented in the CRF as well as the subject's hospital notes. The Principal Investigator must allow the Monitor access to the secure facility where the study devices are stored during the clinical trial in order to check inventory. At the end of the clinical trial all unused study devices must be returned to Johnson & Johnson Medical Korea with the appropriate study device return form. If this is as a result of a Product Complaint for the study devices, the Product Complaint form must be completed.

11.0 STUDY SCHEDULE

11.1 VISIT 1 – SCREENING

The screening activities for this visit may occur over several dates within 5 weeks prior to day of ablation.

Subjects will be evaluated according to the Investigator's standard of care practice. Subjects will be selected for microwave ablation based on the pre-procedure investigations and the Investigator's interpretation of the clinical picture. Eligible subjects will be provided with the study information including the ICF.

The following screening activities will occur prior to the study procedure:

- The subject must be given ample time to review and sign the ICF;
- Collection of demographic information (age at time of consent, gender, race, ethnicity);
- Review and collection of medical and surgical history including current medical conditions (note: HCC diagnosis does not need to be reported as medical history);
- CT Scan of the liver (within 37 days prior to the screening visit)- the subject does not need to repeat a CT scan of the liver at the screening visit if the CT scan based on SOC was done within 30 days prior to the screening visit date;
- Ultrasound of the liver for planning of the ablation procedure (on the day of the visit or up to 7 days prior to the screening visit);
- Laboratory tests (within 37 days prior to the screening visit)- the subject does not need to repeat the following laboratory tests at the screening visit if these tests based on SOC were done within 37 days prior to the screening visit date:
 - Alpha-fetoprotein (AFP) test;
 - Prothrombin Induced by Vitamin K Absence or Antagonist-II (PIVKA-II);
 - Coagulation test (PT, APTT, and INR);
 - Liver function test (AST, ALT, GGT, albumin, indirect, direct and total bilirubin, total protein);
 - Renal function test (BUN, Creatinine and electrolytes (sodium, potassium, and chloride));
 - Complete Blood Count (CBC) (differential cell count and platelet count);
 - Pregnancy test- for women of child bearing potential only.
- Tumor details (size, type, location) and BCLC Staging (pre-procedure staging);
- Evaluation of ECOG Performance Status and Child-Pugh score;
- Collection of concomitant medications (including any medication taken within 30 days prior to the screening visit);
- Review/collection of inclusion/exclusion criteria and determination as to whether the subject is eligible for participation (retrospective data, per site SOC, is permitted to determine eligibility).

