Statistical Methods:	
Categorical variables will be summarized descriptively by frequencies and associated percentages. Continuous variables will be summarized descriptively by number of subjects, mean, standard deviation, median, minimum, and maximum. Confidence intervals will also be provided for procedure-related variables.
 
The number and percentage of subjects achieving Technical Success will be summarized and an exact 95% confidence interval will be estimated. A similar summary will be provided for Primary Technique Efficacy, as well as for the primary and secondary efficacy rates as previously defined.
 
Local tumor progression rates at 1, 3, 6, 9, 12, 18, 24, 30 and 36 months will be estimated using the Kaplan-Meier method and 95% confidence intervals will be provided.
 
The number and percentage of subjects experiencing adverse events (AEs) will be summarized at the preferred term level using the Society of Interventional Radiology (SIR) clinical practice guidelines for event categorization.
 
Two analyses of study data are planned. The first will occur after 30 subjects have completed the 3-month visit and is intended to provide an initial estimate of device effectiveness for Technical Success as well as to summarize the peri-operative out to 3-month post-operative safety

	
profile of subjects undergoing microwave ablation. There are no plans to use the results of the first analysis for the purpose of stopping the study early. The second analysis will occur after all subjects have completed study participation.

--	--

Table 1: Schedule of Events

Visit No. Visit	Visit1: Screening	Visit2A Pre-Ablation	Visit2B Ablation	Visit2C Post-Ablation	Visit3 1 month	Visit4 3 months	Visit5 6 months	Visit6 9 months	Visit7 1 year	Visit8 18 months	Visit9 2 years	Visit10 30 months	Visit11 3 years	USV Unscheduled Visit ⁸
Interval Windows	Within 5 weeks before ablation	-2 to 0 days	Day 0= Ablation of index tumor	0 to 4 days	1 month (+/- 14 days) after ablation	3 months (+/-28days) after ablation	6 months (+/-28 days) after ablation	9 months (+/-28 days) after ablation	12 months (+/-28 days) after ablation	18 months (+/-28 days) after ablation	24 months (+/-28 days) after ablation	30 months (+/-56 days) after ablation	36 months (+/-28 days) after ablation	NA
Study Activity														
Informed Consent	X													
Demographic Information	X													
Medical/Surgical History	X													

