4.0 INTRODUCTION

The Neuwave Medical Certus 140™ 2.45 GHz Ablation System and Accessories consist of Software version 2.1.X and the accessories CertusPR, CertusLK, CertusLN and CertusSR ablation probes and CertuSurgGT Surgical Tool. A dual probe clip and several accessories designed to allow for the mechanical interfacing of the Power Distribution Module (PDM) to a variety of vendors' CT Tables are also available. These accessories are ease-of-use and convenience accessories that do not impact the clinical functionality of the system and thus are not described in detail.

The Certus 140™ 2.45 GHz Ablation System and Accessories form a Microwave Ablation System which is intended to ablate/coagulate soft tissue. The Certus 140™ Microwave Ablation System and Accessories are a general purpose thermal ablation tools used by physicians to ablate soft tissue lesions in a wide variety of tissue and disease states. The Certus 140™ 2.45 GHz Ablation System and Accessories are currently cleared by the United States (US) Food and Drug Administration (FDA) and has been in clinical use since 2011 in the United States. The most common applications by clinicians have been the ablation of liver, kidney and lung lesions. Additional, but less common uses have been the ablation of soft tissue lesions in bone and nerve ablation.

This study is a single arm prospective trial to evaluate the safety and effectiveness of microwave ablation in patients with hepatocellular carcinoma in Korea of at least 19 years of age. Pre-clinical and clinical data has shown that microwave ablation is safe and effective in liver tumors with low complication rates, high rates of technical success, lower rates of local tumor progression and promising disease-free and overall survival rates than have historically been reported for radiofrequency (RF).

The Certus 140™ Microwave Ablation System and Accessories is contraindicated for:

- Use in cardiac procedures
- Pregnant patients – *potential risks to patient and/or fetus have not been established*
- Patients with implantable pacemakers or other electronic implants. *Implanted electronic devices may be adversely affected by microwave power*
- Use on the central nervous system
- Endometrial applications

Refer to the Certus 140™ Microwave Ablation System and Accessories accompanying documents for a list of Warnings and Cautions.

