8.2 EXCLUSION CRITERIA

Subjects will be excluded from the study for any of the following:

1. Active (subject currently receiving systemic treatment) bacterial infection or fungal infection;
2. Systemic administration (intravenous or oral) of steroids, including herbal supplements that contain steroids, within 30 days prior to the study procedure;
3. Chemotherapy or radiation therapy for hepatocellular carcinoma may not be performed for 30 days prior to the study procedure;
4. Subject with implantable pacemakers or other electronic implants;
5. Planned/ scheduled liver surgery;
6. Subject with a platelet count of less than 50,000/mm³;
7. Subject with an INR greater than 1.5;
8. Subject with renal failure on renal dialysis;
9. Scheduled concurrent procedure other than microwave ablation in the liver;
10. The subject is a female who is pregnant or breastfeeding;
11. Physical or psychological condition which would impair study participation;
12. Participation in any other clinical study concurrently or within the last 3 months;
13. The subject is judged unsuitable for study participation by the Investigator for any other reason; or
14. Unable or unwilling to attend follow-up visits and examinations.

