11.2 VISIT 2A – PRE-ABLATION

The following data must be collected prior to the study procedure:

- Quality of Life questionnaires: VAS pain score, EORTC QLQ-C30 and EORTC QLQ-HCC18;
- Any update to medical/ surgical history;
- Any update to concomitant medications;

- Laboratory tests:
 - Prothrombin Induced by Vitamin K Absence or Antagonist-II (PIVKA-II);
 - Coagulation test (PT, APTT, and INR);
 - Liver function test (AST, ALT, GGT, albumin, indirect, direct and total bilirubin, total protein);
 - Renal function test (BUN, Creatinine and electrolytes (sodium, potassium, and chloride));
 - Complete Blood Count (CBC) (differential cell count and platelet count);
- Evaluation of ECOG Performance Status and ASA score;
- Confirm inclusion and exclusion criteria;
- Date and time of hospital admission.

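### Section 11.1 puts the only pregnancy test in the visit text under a 37-day look-back and Visit 2A lists none, so the required result can be up to 72 days old at ablation in the extreme case (35 days on a narrower reading)

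*Combined protocol and SAP*

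**What the plan says.** **The contraindication and the criterion.** Section 4.0 lists pregnant patients among the device contraindications, adding "potential risks to patient and/or fetus have not been established". Section 8.2, exclusion 10, reads "The subject is a female who is pregnant or breastfeeding".

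**Screening.** Section 11.1 says "The screening activities for this visit may occur over several dates within 5 weeks prior to day of ablation", and Table 1 gives the same Visit 1 window, "Within 5 weeks before ablation". The laboratory item opens with "Laboratory tests (within 37 days prior to the screening visit" and waives repetition of the tests listed below it if "these tests based on SOC were done within 37 days prior to the screening visit date". The last test on that list is "Pregnancy test- for women of child bearing potential only". The section also allows retrospective standard-of-care data to be used for eligibility.

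**Immediately before ablation.** Section 11.2 (Visit 2A, day -2 to day 0 in Table 1) includes "Confirm inclusion and exclusion criteria". Its laboratory list is PIVKA-II, coagulation with INR, liver function, renal function, and blood count with platelets. There is no pregnancy test. None appears among the pre-procedure tests in section 9.1 or in section 11.3 (Visit 2B).

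**Table 1.** The note on the pregnancy test says who is tested and gives no timing. It stands apart from the note that carries the 37-day laboratory look-back. As extracted, the pregnancy row has marks at Visits 1 and 2B and a blank at Visit 2A.

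**The concern.** The plan re-checks eligibility just before treatment and, for two laboratory-based exclusions (6, platelets; 7, INR), supplies fresh results at that step. Exclusion 10 also has a designated test, but the visit text requires it only at screening and allows an older routine result to serve. A site can follow sections 11.1 and 11.2 to the letter and complete the Visit 2A confirmation with no recent pregnancy result.

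What is at stake is subject safety. No endpoint estimate or confidence interval depends on this. Ablation is performed under general anesthesia, with contrast-enhanced MRI and CT afterwards for all subjects (section 9.1 and the Table 1 notes), and the protocol itself says the risks in pregnancy are not established. Neither section 8.1 nor section 8.2 has a contraception requirement that would cover the interval between test and procedure.

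**Working it through.** The documents state no maximum age for the pregnancy result, so there is no figure to reproduce. The maximum follows from adding the protocol's own windows.

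**Inputs**
- Look-back before the screening visit: L = 37 days (section 11.1).
- Longest interval from screening visit to ablation: S = 5 weeks = 5 × 7 = 35 days (section 11.1; Table 1).
- Visit 2A: k = 0 to 2 days before ablation (Table 1).

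**Reading A: look-back counted from the screening visit, as section 11.1 words it**
- Maximum age at ablation = L + S = 37 + 35 = 72 days (72 / 7 = 10.3 weeks).
- Maximum age at the Visit 2A confirmation = 72 - k, that is 70 days (Visit 2A on day -2) to 72 days (day 0).

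**Reading B: the 5-week sentence also limits the tests**
- Maximum age at ablation = S = 35 days; at Visit 2A, 35 - 2 = 33 to 35 days.
- This reading fits the text less well. If no result could be more than 35 days before ablation, none could be more than 35 days before a visit that itself precedes ablation, and a 37-day allowance would never have any effect.

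**Comparison with exclusions 6 and 7.** Platelets and INR are drawn at Visit 2A, so those results are at most 2 days old at ablation.

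**What Table 1 can settle.** The extracted pregnancy row has the same pattern of marks as every row from CT scan to ASA score: Visit 1 marked, 2A blank, 2B onward marked. That pattern conflicts with intact text. PIVKA-II and ASA score are collected at Visit 2A under section 11.2, yet both cells are blank there. The row is probably damaged in extraction, so neither the mark at 2B nor the blank at 2A is evidence.

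| Place | Pregnancy test | Timing |
|---|---|---|
| 4.0, 8.2 | contraindication; exclusion 10 | not tied to a test |
| 11.1 | listed | 37-day look-back from a visit up to 35 days before ablation |
| 11.2 (2A) | not listed | eligibility confirmed here |
| 9.1, 11.3 (2B) | not listed | none |
| Table 1 note | listed | none given |
| Table 1 row | unreliable as extracted | check original |

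**The case against.** - **Table 1 may already schedule a test around the procedure.** The extracted row does carry a mark at Visit 2B, the day of ablation, and no passage says the visit text overrides the schedule. This stands as a reason to read the original table. If it shows a mark at 2A or 2B, the fault is a disagreement between table and text rather than a missing test, and reconciliation is still needed.
- **The Table 1 notes do not clearly put this test under the 37-day rule.** Correct: only the list in section 11.1 does so. Whether the look-back is meant to apply is therefore an open question for the sponsor.
- **72 days is a corner case.** Also correct. It needs a routine result at the far edge of the look-back and a visit at the far edge of its window. Under Reading B the limit is 35 days. The Visit 2A confirmation lacks a listed current result under either reading.
- **Not every criterion is re-measured at Visit 2A.** Child-Pugh and BCLC stage are not on the section 11.2 list either, so one missing item is not in itself a contradiction. The point here is narrower: a stated waiver lets a device contraindication be cleared on an old result, while other laboratory exclusions are refreshed.
- **A reader might infer that Visit 2A could not detect a pregnancy.** The documents do not support that. Section 11.2 also asks for updates to medical history, exclusion 10 is not tied to a test result, and the investigator may test again. Testing is not required; detection is not ruled out.

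**Conclusion.** The point holds, within limits. On the visit text, the required pregnancy result can be up to 72 days old at ablation in the extreme case, or 35 days on the narrower reading. The Visit 2A confirmation of exclusion 10 has no pregnancy test listed alongside it. A reader might go further and conclude that no test near the procedure is scheduled anywhere; that cannot be said until the original Table 1 row has been read.

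Few subjects are affected. The documents give no share of women of child-bearing potential. Assuming 0 to 10% of the 30 planned subjects, that is 0 to 3 women (30 × 0.10 = 3), possibly none. The point deserves correction because it concerns a contraindication that the protocol states itself and the correction is small. The analysis is not touched.

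**What to change.** Check the pregnancy row in the original Table 1. Then reconcile section 11.1, section 11.2, the Table 1 row and notes, exclusion 10 and the section 4.0 contraindication, so that the stated timing of the test and the Visit 2A eligibility confirmation agree. In doing so, state whether the 37-day look-back is meant to apply to the pregnancy test, and whether the 5-week window limits the tests or only the visit. The timing is for the sponsor's clinical team to set; none is proposed here.

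The cost is a few lines of text in the affected sections and notes and, depending on the timing chosen, at most a repeat test for women of child-bearing potential.
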